Title: Smoking Cessation Pilot for People Living With HIV (PLWH)

NCT Number: **NCT04808609**

Document Date: 6/1/2021

Stand Alone Protocol: SMOKING CESSATION PILOT – IRB-AAAS6990

PI: [name]

Background:

Of the approximately one million persons living with HIV (PLWH) in the United States (U.S.), it is estimated that between 40-70% smoke cigarettes, at least three times the prevalence (14%) observed in the general U.S. adult population. Consequently, PLWH experience substantial tobacco-related morbidity and mortality. In PLWH, after achieving and maintaining a suppressed viral load, smoking cessation is the next most important health behavior to maximize both quality of life and life expectancy. Indeed, PLWH who quit smoking upon entering HIV care gain greater than 5 years of life expectancy as compared to those who enter HIV care and continue smoking.

Given the high prevalence of cigarette smoking among PLWH and the benefit of smoking cessation, there is an urgent need for swift action to intervene to reduce tobacco use rates. However, evidence to improve tobacco cessation among PLWH is inadequate. Few tobacco cessation interventions have been tested among PLWH, and of those which have, there is 'very low' quality evidence that tobacco cessation interventions were effective in the short-term, and 'moderate' quality evidence indicating similar outcomes to controls in the long-term.₃ Given the few randomized controlled trials (RCTs) examining smoking cessation interventions for PLWH, and the major methodological limitations of many of these studies (e.g., lack of randomization, comparison conditions, treatment fidelity assessments, abstinence verification tests), it is critical to develop evidence-based tobacco cessation interventions to address the complex and unique needs of PLWH (e.g., risk factors, treatment needs). Tailored cessation studies designed for dissemination and implementation are necessary to focus efforts on PLWH who use tobacco products.

Pharmacotherapy Offered to All Participants. Current treatment guidelines recommend pharmacotherapy be offered to all smokers making a quit attempt.₄ Pharmacotherapy doubles quit rates when compared to placebo,₅ and the highest abstinence rates are achieved when pharmacotherapy is combined with a behavioral intervention.₆ There are also ethical concerns about offering a placebo treatment only in a historically mistreated group;₇₋₉ therefore, the interventions would likely be less acceptable or feasible if a placebo was part of the study design. As part of this intervention, we will provide all participants with NicoDerm CQ Patch as a form of Nicotine Replacement Therapy. As all forms of nicotine replacement therapy are over-the-counter medications, participants are not required to obtain physician clearance to take them.

Mobile health (mHealth) is an ideal platform for implementation and dissemination of evidence-based strategies.₁₀ mHealth can provide mechanisms for improving the efficiency and effectiveness of care provided while reducing administrative burden. mHealth technology can be used for achieving health equity in vulnerable groups because it is a widely available and relatively inexpensive tool for health behavior change and can be ₁₁ adapted to meet the needs of its end-users.₁₂₋₁₅ The emerging evidence base on mHealth delivered behavioral interventions supports their promise to improve health disparity outcomes.₁₆ Therefore, mHealth interventions such as Lumme proposed through this study is timely, relevant, scalable and likely to improve health outcomes in our health disparate study population -- PLWH who smoke.

Aim: To conduct a pilot study on the Lumme mobile app in a population of PLWH as a tobacco cessation intervention (N=40) Hypothesis 1:

Overview of Study Aims, Design and Methods

Purpose: The purpose of the research study is to find out more about smoking behaviors in people living with HIV and the subsequent efficacy of tobacco cessation strategies.

Study Design: A pilot study will be conducted with 40 PLWH randomized to 2 arms. Participants will be randomly assigned to receive Lumme (active) or a control condition (standard smoking cessation counseling session). Participants will also receive a survey at baseline and at 12-weeks post-baseline.

Recruitment: We will recruit PLWH by posting flyers at local clinics and community-based organizations throughout New York City. Potential participants will be pre-screened for eligibility over the phone by study staff. We will also provide enrolled participants with a study flyer to share with potentially eligible individuals.

Study Populations: Our study participants will consist of 40 individuals who smoke tobacco. Inclusion criteria. (1) PLWH; (2) \geq 18 years of age; (3) own an Android smartphone; (4) understand and read English; (5) not pregnant or breastfeeding; (6) permanent contact information; (7) smokes \geq 5 cigarettes per day for the past 30 days; (8) interested in quitting smoking within 30 days; and (9) blow >5 CO into a breath analyzer at baseline. Exclusion criteria. (1) self-report being HIV-negative or unknown status; (2) pregnant, breastfeeding, or planning to become pregnant during the study period; (3) planning to move within 3 months of enrollment; (4) a positive history of a medical condition that precludes use of the nicotine patch; (5) current use of nicotine replacement therapy or other smoking cessation medications (e.g., Chantix or Zyban); (6) current enrollment in another smoking cessation program; and (7) blows \leq 5 CO into a breath analyzer at baseline.

Screening: Potential study participants will provide verbal informed consent to complete a phone screening that assesses eligibility. If eligible, participants will attend a baseline session described below. Those who do not screen eligible will be informed and thanked for their time.

Procedures: Eligible participants up to this point will be scheduled to attend a baseline visit at the Columbia University School of Nursing. Prior to arriving, participants will be asked to complete the Fagerstrom Test for Nicotine Dependence (FTND) and identify their cigarette type (menthol vs regular). Upon arrival to the study site, scheduled participants will be asked to blow into a breath analyzer to complete determining study eligibility. Breath samples will be analyzed for exhaled carbon monoxide (CO) levels (in ppm) using a breathalyzer (Micro +TM basic Smokerlyzer®). Those identified as ineligible will be given a Metrocard to thank them for their time. Those identified as eligible will be given an informed consent form and the study staff will read the form to them. Before a participant signs the informed consent form, staff will answer any questions. Participants will be given a copy of the informed consent form for their records.

After providing written consent, study participants will complete a timeline follow back to track their cigarette use for the last 30 days. Afterwards, they will complete a baseline questionnaire that includes demographic characteristics, tobacco use history, substance use history, alcohol use history, psychosocial factors, pharmacotherapy use, and more (See Table 1). Survey instruments will be collected through Qualtrics, a secure, Web-based application designed to support data capture for research studies, providing an intuitive interface, audit trails, and automated export. Qualtrics is a free service offered through Columbia University Irving Medical Center.

Following the completion of the baseline study instruments, study participants be randomized (1:1) to the Lumme arm or the control arm. Participants in both arms will undergo a smoking cessation counseling session and be provided with nicotine replacement therapy (NRT) in the form of the NicoDerm CQ Patch, under the supervision of a nurse. They will be provided

NRT sufficient for an 8-week supply in order to follow the three-step program. However, they will be encouraged not to begin NRT until 2-weeks after the baseline visit. This will be the quit date set for participants in both arms.

Participants who smoke more than 10 cigarettes per day will receive the following dosage: one 21 milligram patch per day for 4 weeks; one 14 milligram patch per day for 2 weeks; and one 7 milligram patch per day for 2 weeks. Participants who smoke 10 or less cigarettes per day will receive the following dosage: one 14 milligram patch per day for 6 weeks; and one 7 milligram patch per day for 2 weeks. This is considered the standard clinical treatment and participants will receive additional instructions on usage of the patch. Subjects will be told the risks of using the patch, which include skin irritation, itching, dizziness, headache, rapid heartbeat, and nausea. Participants will also be advised that they can curb additional cravings with their choice of gum or lozenge available for purchase overthe-counter.

For those in the intervention arm, study staff will provide participants with a Misfit Vapor 2 or Skagen Falster 2 smartwatch and initiate the Lumme app on the participant's mobile phone. Both smartwatches are compatible with the Lumme app. Participants will be asked to wear the smartwatch and use the app for 12 weeks to collect baseline data and improve detection of smoking. Study staff will help users create an account with the Lumme app which will passively collect smoking data during the first 2 weeks, such as when the user smokes (time of day, day of week, before/after eating, after waking up/before going to sleep, before driving to/from work, while driving), where the user smokes, and who is nearby when the user smokes (based on the seeing the same Bluetooth static address as Lumme does not collect identities). Once created, the Lumme app will be paired with the smartwatch so that smoking will be detected by the smartwatch and be sent directly to the Lumme app. The smartwatch will detect cigarettes smoked throughout the time the user wears the smartwatch, or users can manually enter a smoking session. The Lumme app will then be able to reliably predict cravings, target users with notifications to prevent individuals from smoking, refine the notifications for each user, and display their change in smoking behavior and money saved in a smoking diary. Users will also be able to see their quit plan with their assigned quit date 2 weeks after baseline, along with smoking trends, supporting tips, and earn badges from the amount of money saved. Data related to participants' smoking behaviors and patterns will be shared with Lumme. The study coordinator will also be able to access smoking behaviors and subject information through Lumme's anonymized online dashboard. At the end of the baseline visit, all enrolled participants will be compensated \$40 for their participation in the form of a pay card.

On the day before their quit date, study staff under the supervision of a nurse will call participants in both arms to remind them of their quit date and to start using their NRT NicoDerm CQ patches the morning of their quit date. This phone call will consist of the staff reassuring and encouraging the participant to stick to their quit date. Specific details for the call will be provided to staff via a phone script.

Upon reaching their quit date, participants in the intervention arm will receive personalized feedback in the Lumme app. Also, participants in both the control and intervention arm will receive biweekly checkin calls from study staff members. Staff will complete these calls in order to 1) track participants reported NRT fidelity, 2) provide technology assistance to those in the intervention arm who might experience difficulties with the smartwatch or app, and 3) keep participants engaged in the study.

Table 1. Study Measures

Construct	Measures (if applicable)	Measurement Time Points
Demographics	Gender, age, education, income, employment, health insurance, housing, time since diagnosis with HIV, tobacco, alcohol, substance use, health literacy (measured by Short Test of Functional Health Literacy in Adults [S-TOFHLA]), ₁₇ and co-morbid conditions	Baseline
Tobacco Use History	Age of initiation, current smoking, daily smoking, types of products used (e.g., menthol cigarettes, e-cigarettes), history of quit attempts, prior use of quitline/telephone counseling services	Baseline
Tobacco Cessation	CO lung/blood concentration, 7-day point prevalence abstinence –Timeline follow-back (TLFB) _{18,19} ; number of quit attempts; days of continuous abstinence	Baseline, 12 weeks
Illicit Substance and Alcohol Use	NIDA ASSIST _{20,21} , Short Michigan Alcoholism Screening Test (SMAST), Drug Abuse Screening Test (DAST)	Baseline
Health-Related Quality of Life	PROMIS-29 ₂₂	Baseline, 12 weeks
Predictors of Tobacco Cessation	Fagerstrom Test for Cigarette Dependence,23 Readiness to quit24	Baseline, 12 weeks
Cravings and Withdrawal	Minnesota Withdrawal Scale,25	Baseline, 12 weeks
Marker of HIV/AIDS immune status/ ART Adherence	Case Adherence Index (self-report) ₂₆	Baseline, 12 weeks
Intervention Quality	Health Information Technology (IT) Usability Evaluation Scale (Health- ITUES) ₂₇ ; Post-System Study Usability Questionnaire (PSSUQ) ₂₈ , Intervention ratings	12 weeks
Psychosocial Factors	Stress: Perceived Stress Scale (PSS) _{29,30} , Depression: Center for Epidemiological Studies Depression scale (CESD score) ₃₁ , Anxiety: State-Trait Anxiety Inventory (STAI score) ₃₂ , Social support ₃₃	Baseline, 12 weeks
Pharmacotherapy use	Nicotine replacement therapy, Bupropion, Varenicline Use and Self-Reported Adherence	Baseline, 12 weeks

At 12 weeks after the baseline visit, participants will attend a 12-week follow-up visit at the study site. Or if requested, participants can complete a remote study visit, where they will be mailed a CO monitor (by the study team and complete study tasks via video call on Zoom Health with a study team member. Study participants will be asked to report a 7-day point prevalence abstinence of smoking cigarettes and provide a breath sample using Micro _{+TM basic} Smokerlyzer_®. They will also be given a follow-up survey that includes questions asked at baseline and process questions dictated by the primary outcomes that assess the usability and acceptability of Lumme (see Table 1).

At the 12-week follow-up visit, semi-structured in-depth interviews will take place with participants. The in-depth interviews will be approximately 10-30 minutes in length and no additional compensation will be provided. The in-depth interviews will be conducted by the study coordinator and research assistants, the members responsible for conducting follow-up visits. These interviews aim to fill gaps in the literature by taking a qualitative approach to understanding the acceptability of the

Lumme app as a smoking cessation tool in the intervention arm and learn more about all participants' opinions on the recruitment and enrollment process. Both groups will answer questions including: 1) How would you modify the outreach and recruitment process to improve it or make it easier? 2) How comfortable were you with the recruitment, screening and enrollment process? 3) How can we improve the current screening process? Some of the questions the questionnaire will include for the intervention group are: 1) Please describe your general perceptions and expectations of the app, 2) How often did you use the app? 3) How helpful was the app for tobacco cessation?

The team will adhere to qualitative research processes to ensure the credibility, confirmability, dependability, and transferability of the qualitative data from these analyses.₃₄ To support the credibility of the data, we will conduct peer debriefing and triangulate findings across multiple data sources (surveys). In addition, we will use "member checks," i.e., sharing of initial data interpretations with participants to ensure accurate interpretations. Triangulation of findings, along with reflexivity, will enhance the confirmability of the interpretations. The investigators will carefully record an audit trail and keep extensive field notes to facilitate transferability of study findings into other contexts. At the end of the 12-week follow-up visit, participants will be compensated \$60 for their participants will also receive a Metrocard at each in-person visit.

Operationalization of Outcome Measures: The primary outcome for determining preliminary efficacy will be biochemically validated 7-day point prevalence abstinence.

Analysis: This is a pilot study meant to assess preliminary feasibility, acceptability, and efficacy. Given the small sample size, the purpose of the arms is simply to monitor for unexpected, gross differences between arms.

To determine acceptability, we will ask participants in both arms how useful each of the intervention components are (1 = *Not at all useful* to 7 = *Extremely useful*) and whether they would recommend the program to a friend (1 = *Definitely would not recommend* to 7 = *Definitely would recommend*). For the intervention to be deemed acceptable, the mean level for each of these measures would have to be five or higher.

All in-depth interviews will be transcribed verbatim and then coded. The development and application of a coding scheme is an integral component of the data analysis process. It enables the systematic examination and interpretation of the data related to the primary analytic foci. The coding scheme is conceptualized as a multilevel structure. At the highest level are the primary analytic foci coded as headings. Specific aspects or dimensions of the headings are assigned core codes. Specific aspects or dimensions of the core codes are assigned sub codes. We use ATLAS.ti, a software program for qualitative analysis, to facilitate the analysis.

The following 7 steps will be used to develop the coding scheme:

- Step 1: Identify the principal issues discussed by interviewees.
- Step 2: Construct definitions of the primary analytic themes.
- Step 3: Develop and apply core codes and sub-codes to the initial set of interviews.
- Step 4: Develop a provisional coding scheme.
- Step 5: Test and refine the provisional coding scheme.

Step 6: Reconcile coding differences and construct an updated and final coding scheme. Step 7: Apply the coding scheme to the full data set and assess inter-coder reliability.

After all transcripts have been coded, we will extract and examine the content of text segments linked to core codes and sub-codes relevant to understanding the technology acceptance of the Lumme app and barriers and facilitators to its use. Based on the coded data, we will propose ways in which certain themes are analytically related. A careful examination of the coded text will reveal the associations among these themes, and may lead to more refined data searches. Once we establish patterns of relationships among themes and issues, we will identify participants' accounts that support or refute these patterns. Identifying and accounting for cases that deviate from an interpretative pattern enable us to test and confirm the pattern's validity and robustness. [name] has done extensive work understanding technology acceptance with particular emphasis on end-users' needs. ³⁵⁻³⁸

Efficacy of the intervention will be based on self-reported 7-day point prevalence abstinence at the follow-up survey. Lost-to-follow-up participants will be included as smokers. The abstinence rate will be calculated.

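### Does the plan's silence on how the allocation sequence is generated and concealed leave the comparison of arms open to steering?

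*Combined protocol and SAP*

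**What the plan says.** Study Design fixes the size and the random assignment: "A pilot study will be conducted with 40 PLWH randomized to 2 arms", followed by "Participants will be randomly assigned to receive Lumme (active) or a control condition". Procedures adds the ratio and the timing: "study participants be randomized (1:1) to the Lumme arm or the control arm". Randomization comes after the breath carbon monoxide eligibility check, after written consent, and after the baseline instruments.

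The staffing around that step is described in general terms. Under Recruitment, "Potential participants will be pre-screened for eligibility over the phone by study staff". Procedures then says "Eligible participants up to this point will be scheduled to attend a baseline visit", without naming who does the scheduling. Study staff read out the consent form and answer questions about it. After assignment, for the Lumme arm, "study staff will provide participants with a Misfit Vapor 2 or Skagen Falster 2 smartwatch and initiate the Lumme app", and staff later give technical help to that arm on the check-in calls.

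Nowhere do the documents give the type of sequence, any blocks or strata, the holder of the list, or the means of concealment. Qualtrics is described for survey capture only. On the role of the comparison, the Analysis section says that "the purpose of the arms is simply to monitor for unexpected, gross differences between arms".

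**The concern.** Randomization protects a comparison only if the people who decide who enters, and when, cannot foresee the next assignment. Staff here cannot be blind to arms already assigned, because one arm receives a watch and an app and the other does not. The documents do not separate recruiting from holding the list. If the next arm were known, people judged readier to quit, or easier to set up with the app, could be booked or encouraged into Lumme places. Such an error is systematic and more participants would not remove it. It could create or hide the kind of difference that the arms are there to reveal.

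The Background sharpens the point by criticising earlier work for "major methodological limitations of many of these studies (e.g., lack of randomization". A reader might expect a trial that makes this criticism to set out its own method in full.

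**Working it through.** The plan gives no error rate, power, effect size or abstinence rate, so there is no figure of its own to reproduce. The check has two parts: what the text rules in or out, and how large the effect of foreseeable allocation could be.

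**The text.**

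- Stated: random assignment, 1:1, 40 people, two arms, after eligibility, consent and baseline measures.
- Not stated: generation, custody, concealment.
- Not present: any rule that would make allocation predictable, such as alternation, a posted list or small fixed blocks.

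The late timing keeps baseline answers free of any influence from the revealed arm. By itself it does not stop someone who already knows the next arm from influencing who is booked.

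**How predictable each method would be.** From the documents: 40 people, taken as 20 per arm. Suppose staff see all past assignments, know the block size and guess optimally. For a block of 2n, the expected share of correct guesses is

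p = [n + 2^(2n−1)/C(2n,n) − 0.5]/(2n).

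- Block of 4 (n = 2): (2 + 8/6 − 0.5)/4 = 0.708.
- One shuffled list of 40 (n = 20): (20 + 3.988 − 0.5)/40 = 0.587.
- Simple randomization from a hidden list: 0.500.
- Open list: 1.000.

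**Shift in the arm difference.** Let d be the amount by which people steered to an expected Lumme place quit more often than the others. It is assumed to lie between 0 and 20 points; the documents give nothing on it. With no true effect, and every guess acted on, the shift is (2p − 1) × d. At d = 20 points:

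| Method | Shift (points) |
|---|---|
| Open list | 1.000 × 20 = 20 |
| Blocks of 4 | 0.417 × 20 = 8.3 |
| Shuffled 20/20 list, hidden | 0.174 × 20 = 3.5 |
| Simple, hidden | 0 |

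At d = 0 every entry is zero.

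**Against sampling noise.** At an assumed 20% abstinence and 20 per arm, the standard error of the difference is √(2 × 0.2 × 0.8/20) = 0.126, or 12.6 points.

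**Chance of a false gross difference.** Read gross, as an assumption, as a Lumme lead of at least 4 of 20 (20 points). Exact binomial probabilities with no true effect, splitting the shift evenly around 20%, are:

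| Method | d = 5 | d = 10 | d = 20 |
|---|---|---|---|
| Unpredictable | 8.2% | 8.2% | 8.2% |
| Shuffled 20/20 list, hidden | 9.3% | 10.5% | 13.2% |
| Blocks of 4 | 11.0% | 14.4% | 23.1% |
| Open list | 15.9% | 27.3% | 58.0% |

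Putting the whole shift in the Lumme arm changes the open-list row to 17.0%, 29.0% and 57.3%. The 8.2% itself depends on the assumed rate: 3.2% at 10% abstinence and 11.3% at 30%.

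**The case for a change.** The strongest case for acting is that the omission is real, the remedy is a few sentences and one list, and a reader cannot confirm concealment from a ratio and a time point. Phone screening, booking and the consent talk all leave room for discretion. The comparison also carries an outcome labelled preliminary efficacy. All of that stands as a description of what the text leaves out.

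It does not establish a fault in the design. Study staff is a generic term, and the documents do not show that those who screen or schedule are those who set up the watch, or that either group holds the list. The scheduling route to bias is also loose. People respond to flyers or are referred by participants. Someone booked can still fail the breath test or decline consent, so the next person booked need not take the next assignment. Android ownership and interest in quitting within 30 days are entry criteria for everyone, which narrows the differences staff could act on. Steering at the consent talk remains possible, but only for someone who already knows the next arm.

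The Background remark concerns studies that lacked randomization. This trial randomizes, so the remark does not count against it.

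**Conclusion.** The concern correctly identifies missing detail, but it calls for no change. The plan commits to 1:1 random assignment at the right moment. Carrying that out with a hidden list is ordinary practice and fully consistent with the text. No stated instruction would produce predictable allocation.

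The alarming figures, up to a 20-point shift and a 58% chance of a false 20-point lead, need four things together: an open list, steering at every place, a 20-point difference in quitting between those steered and the rest, and 20% abstinence. None is in the documents. Under a hidden shuffled list the same extreme steering moves the chance of a false lead from 8.2% to 13.2%. Under simple hidden randomization it does not move.

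The use made of the comparison limits the stakes further. The Analysis section treats this as a small pilot, specifies no between-arm test, and ends by saying only that an abstinence rate will be calculated. The acceptability ratings and interviews do not rest on a concealed comparison. How the list was made, who held it and when each assignment was released belong in the trial file and the eventual report. The conclusion would differ if those records showed an open or alternating list.

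### Does the missing look-back for quit attempts and days of continuous abstinence at week 12 need a change to the plan?

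*Combined protocol and SAP*

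**What the plan says.** The Tobacco Cessation row of Table 1 names four things for baseline and 12 weeks: carbon monoxide, seven-day point prevalence abstinence with the timeline follow-back, and then "number of quit attempts; days of continuous abstinence". The last two have no recall period, start date or definition.

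Under Procedures, at the baseline visit, "study participants will complete a timeline follow back to track their cigarette use for the last 30 days". Patch use is to start two weeks after baseline, and of that day the plan says: "This will be the quit date set for participants in both arms".

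At week 12, participants are asked to "report a 7-day point prevalence abstinence of smoking cigarettes and provide a breath sample". The text continues: "They will also be given a follow-up survey that includes questions asked at baseline".

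Between those points, "participants in both the control and intervention arm will receive biweekly checkin calls from study staff members". The stated purposes open with "Staff will complete these calls in order to 1) track participants reported NRT fidelity" and go on to technology help for the intervention arm and keeping people engaged. Recording of smoking is not among them. Smoking is detected continuously only in the intervention arm, through the watch and app.

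**The concern.** A 30-day recall at baseline, followed by a week-12 survey that repeats baseline questions, invites the reading that the 30-day window is used again. The period after the quit date is more than twice that long. Under that reading, someone who lapsed early and quit again before the window opened would look the same as someone abstinent since the quit date, and early quit attempts would go uncounted. Those are the distinctions that these two measures can make and seven-day abstinence cannot.

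Nothing else scheduled in both arms fills the interval. The watch and app cover one arm, the calls have other stated purposes, and a breath sample at week 12 says nothing about the weeks just after the quit date. Smoking status in that period cannot be collected prospectively once it has passed. Two open items therefore seemed worth fixing: the look-back itself, and the lack of a shared smoking measure between the quit date and week 12.

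**Working it through.** The plan states no figure of its own here, so the check is day arithmetic on its schedule, followed by a reading of what depends on the result.

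**Inputs.** Baseline is day 0. The quit date is 2 × 7 = day 14 (Procedures). Follow-up is 12 × 7 = day 84 (12-week visit). The baseline follow-back is 30 days (Procedures). The patch supply is 8 weeks from the quit date (Procedures).

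**Period after the quit date.** 84 − 14 = 70 days.

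**If the 30-day window were reused at week 12 (assumption).**
- It opens on day 84 − 30 = 54, or 54/7 = 7.7 weeks after baseline.
- It covers 30/70 = 43% of the period and misses 70 − 30 = 40 days, 40/70 = 57%.
- The patch supply runs from day 14 to day 14 + 56 = 70, so the window covers 70 − 54 = 16 of 56 supply days, 16/56 = 29%.

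**If the period starts at the quit date or at baseline.** It is 70 or 84 days, and no day after the quit date is missed.

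**If days of continuous abstinence means time since the last cigarette.** No window applies, and the 30-day cap disappears.

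The possible loss therefore runs from 0 to 57%, depending on a reading the plan does not state. Three features of the text bear on which reading is likely:

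1. In Table 1 the follow-back is attached to seven-day point prevalence. Quit attempts and continuous abstinence come after it as separate items, divided by semicolons.
2. At baseline the follow-back is a step completed before the questionnaire. The week-12 sentence about repeating baseline questions concerns the survey, so it need not carry the 30-day follow-back forward.
3. Table 1 is a list of instruments. It gives no recall period for stress, depression, withdrawal or treatment adherence either. Such wording may sit in the survey itself, which is not among these documents.

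**What depends on it.** The Analysis section covers acceptability ratings, coding of interviews, and the seven-day abstinence rate with lost participants counted as smokers. Neither of the two measures appears there. The arms are kept only to watch for gross, unexpected differences.

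**What a call item would add.** Reading biweekly as every two weeks (assumption), calls fall at about weeks 4, 6, 8 and 10. A past-seven-day question at each would cover 4 × 7 = 28 days, 28/70 = 40% of the period. Of these, 7 + 7 + 5 = 19 fall before day 54, so 19 of the 40 days that a 30-day window misses would be covered.

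**The case for a change.** The strongest case for a change is that both gaps are real and cheap to close. No look-back is stated. At least two readings are possible, and they give different data. The investigators chose to list these measures in a pilot that aims at preliminary efficacy. One sentence would make sure both arms are asked about the same period, and one short question in calls that already take place would anchor recall without added visits.

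The factual part of this stands: the text fixes no window, and the arithmetic is right. The need for a change does not follow, for three reasons.

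First, the 57% loss belongs to one reading only, and the layout of Table 1 does not favour it. A team asking about quit attempts at week 12 would naturally ask about the time since the quit date or since enrolment.

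Second, the obvious single rule has limits of its own. A window from the quit date has no counterpart at baseline, where Table 1 also schedules both measures, so the two visits would cover different lengths of time. It also leaves out days 0 to 14, when participants who are already interested in quitting may make an attempt; covering those needs 84 days. The choice is reasonable either way and can be made in the survey wording.

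Third, the call item is a trade-off. The app is there to "display their change in smoking behavior and money saved in a smoking diary", so self-monitoring is part of what the intervention arm receives. Asking controls about their smoking every two weeks could narrow the contrast between arms by an unknown amount, and so put the main comparison at some risk for the sake of two measures with no planned analysis. Measuring smoking at baseline and week 12 only is a clear and defensible schedule for 40 participants.

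**Conclusion.** The look-back is missing, but the plan followed as written gives no wrong result. The primary seven-day abstinence outcome is untouched, and no analysis or decision uses the number of quit attempts or the days of continuous abstinence. The worst case, 40 of 70 days after the quit date unseen and continuous abstinence capped at 30 days, rests on the assumption that the 30-day baseline follow-back is reused at week 12. Under the other natural readings the loss is zero.

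This is detail that the study team can settle when wording the week-12 survey, provided both arms are asked the same thing and any report of the two measures states the period covered. The lack of a shared smoking measure between the quit date and week 12 is a design choice with a fair reason on each side. The conclusion would be different if either measure were given a role in a formal comparison or a go/no-go rule.
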